Appendix B Psoriasis Area Severity Index (PASI)

Shown below is the original description of the PASI (Fredriksson T, Pettersson U. *Dermatologica* 1978;157:238-44) which involves the assessment of erythema (E), infiltration (I), and desquamation (D), and body surface area involvement (A) over 4 body regions (head (h), trunk (t), upper (u) and lower (l) extremities).

Degree of severity (per body region)	Value given
No symptoms	0
Slight	1
Moderate	2
Marked	3
Very marked	4

Surface involved (per body region)	Value given
<10%	1
10-29%	2
30-49%	3
50-69%	4
70-89%	5
90-100%	6

Because the head, upper extremities, trunk, and lower extremities correspond to approximately 10, 20, 30, and 40% of body surface area, respectively, the PASI score is calculated by the formula:

$$\text{PASI} = 0.1(Eh + Ih + Dh)Ah + 0.2(Eu + Iu + Du)Au + 0.3(Et + It + Dt)At + 0.4(EI + II + DI)Al$$

ICH	international conference on harmonisation
IL-6	interleukin 6
IMP	investigational medicinal product
ITT	Intent-To-Treat
IWRS	Interactive Web Response Systems
LOCF	last observation carried forward
LLQ	lower limit of quantification
MCH	mean corpuscular hemoglobin
MCHC	mean corpuscular hemoglobin concentration
MCV	mean corpuscular volume#
MedDRA	medical dictionary for regulatory activities
NCA	non-compartmental analysis
PGA	physician's global assessment
PASI	psoriasis area severity index
PK	pharmacokinetic
PKS	pharmacokinetic-evaluation-set
PP	per-protocol
PT	preferred term
RBC	red blood cell
SAE	serious adverse event
SAP	statistical analysis plan
SAS	Statistical Analysis System
SES	safety evaluation set
SOC	system organ class
t _{max}	time point of maximal plasma concentration
TEAE	treatment emergent adverse event
TNF-α	tumor necrosis factor α
VCS	valid cases set
WBC	white blood cell
WHO	world health organization

1 Overview

This Statistical Analysis Plan (SAP) is issued to provide a comprehensive and detailed description of strategy, rationale, and statistical technique that will be used to evaluate the clinical efficacy and safety of two oral doses of MP1032 (150 mg bid and 300 mg bid) when taken for 12 weeks by patients with moderate-to-severe chronic plaque psoriasis.

The credibility of the study findings will be ensured by pre-specifying the statistical approaches to the analysis of the study data prior to unblinding of the randomization schedule. This SAP is based on the clinical trial protocol number MP1032-CT04, version 2.0 dated October 19, 2018.

1.1 Background / rationale

MP1032 is a small-molecule macrophage modulator currently not available as a registered or approved medicinal product within the borders of the European economic area, the United States, or Japan. Experimental data have shown that MP1032 can inhibit inflammation by reducing Tumor Necrosis Factor α (TNF- α) and Interleukin 6 (IL-6) [1]. MetrioPharm AG is developing MP1032 as an anti-inflammatory compound. The first target indication is psoriasis.

Psoriasis is a relatively common skin condition, affecting 1.5 to 3% of the general population in Europe [2]. Psoriasis can have a particularly negative effect on quality of life, affecting a sufferer's physical, social, and psychological functioning so the need for effective therapies is high. Psoriasis is characterized by outbreaks of skin inflammation interspersed by varying periods of remission. The underlying mechanisms of the inflammatory flares in psoriasis are poorly understood, but the therapeutic potency of anti-TNF- α and anti-IL-17 biologics is evidence of immune modulation's potential to reduce disease severity [1].

However, antibody-based biologics therapies are not optimal therapies for life-long treatment of psoriasis, due to decreasing efficacy over time and relatively high costs. Furthermore, the use of immune-suppressive drugs, such as methotrexate, cyclosporine, or anti TNF- α / IL-12 / IL-17/ IL-23 biologics increases the risk of opportunistic infections and/or requires regular laboratory checks on blood and liver function [1].

MP1032 has been shown to reduce TNF- α and IL-6 levels in vitro (human peripheral blood mononuclear cells and differentiated human promyelocytic leukemia cells), and in vivo, and its anti-inflammatory potential has been shown in mouse and rat arthritis models. Other anti-inflammatory compounds usually exhibit immune-suppressive effects resulting in an increased vulnerability to infections. MP1032, on the other hand, has shown an anti-infective potential in animal infection models.

As a multi-target small-molecule macrophage modulator, MP1032 seems to avoid the problems of tolerance and reduced long-term efficacy that biologics have. An important potential safety advantage of MP1032 lies in the observation from animal models that the compound reduces rather than increases susceptibility to bacterial and viral infections. This may be due to the fact that MP1032 is reducing – rather than completely suppressing – TNF- α and IL-6 levels.

MetrioPharm considers these molecular and safety characteristics along with the ease of an oral therapy over topical therapies as strong arguments for MP1032 to become an effective therapy option in moderate-to-severe psoriasis, where topical agents are not effective enough or too tedious for patients to apply them regularly.

1.2 Objectives

The trial is designed with two primary endpoints as described in the EMA guideline [2].

Table 1 Objectives and endpoints:

Primary objective	Primary endpoint
The primary objective of this trial is to evaluate the clinical efficacy and safety of two oral doses of MP1032 (150 mg bid and 300 mg bid) when taken for 12 weeks by patients with moderate-to-severe chronic plaque psoriasis.	
Efficacy: MP1032 300 mg bid vs. placebo
 
1.1 Percentage of patients who achieve a 75% improvement (response) in their PASI score (PASI 75) at Week 12 (Day 84) compared to baseline in patients treated with 300 mg bid of MP1032 compared to placebo
 
1.2 Improvement (1 or more points on a 7 Point Scale) in PGA at Week 12 (Day 84) compared to baseline in patients treated with 300 mg bid of MP1032 compared to placebo
 
Efficacy: MP1032 150 mg bid vs. placebo
 
2.1 Percentage of patients who achieve a 75% improvement (response) in their PASI score (PASI 75) at Week 12 (Day 84) compared to baseline in patients treated with 150 mg bid of MP1032 compared to placebo
 
2.2 Improvement (1 or more points on a 7 Point Scale) in PGA Score at Week 12 (Day 84) compared to baseline in patients treated with 150 mg bid of MP1032 compared to placebo
 
Safety:
 
3 Incidence of adverse events

Secondary objectives	Secondary endpoints
To evaluate the effect of each oral doses of MP1032 (150 mg bid and 300 mg bid) compared to placebo on the PASI score	
 Percentage of patients who achieve a 50% improvement (response) in their PASI score (PASI 50) at Week 12 (Day 84) compared to baseline in patients treated with 300 mg bid of MP1032 compared to placebo Percentage of patients who achieve a 50% improvement (response) in their PASI score (PASI 50) at Week 12 (Day 84) compared to baseline in patients treated with 150 mg bid of MP1032 compared to placebo Mean PASI score and change from baseline at Week 4 (Day 28), 8 (Day 56), 12 (Day 84) and week 16 (Day 112) Time to achieve PASI 50 and PASI 75
To evaluate the effect of each oral dose of MP1032 (150 mg bid and 300 mg bid) compared to placebo on the PGA score	
 Mean score and change from Baseline at Week 4 (Day 28), 8 (Day 56), 12 (Day 84) and 16 (Day 112) in the PGA
To evaluate the effect of each oral dose of MP1032 (150 mg bid and 300 mg bid) compared to placebo on the BSA	
 Mean value and change from Baseline at Week 4 (Day 28), 8 (Day 56), 12 (Day 84) and 16 (Day 112) in the BSA

Secondary objectives (continued)	Secondary endpoints (continued)
To evaluate systemic exposure of two oral doses of MP1032 (150 mg bid and 300 mg bid) when taken for 12 weeks by patients with moderate-to-severe chronic plaque psoriasis	
 PK data analysis

1.3 Modifications from the statistical section in the protocol

Not applicable.

2 Investigational plan

2.1 Study design and randomization

This trial is a randomized, double-blind, parallel, placebo-controlled trial to evaluate the efficacy and safety of two oral doses of MP1032 (150 mg bid and 300 mg bid) in adult patients with moderate-to-severe chronic plaque psoriasis.

The trial design consists of a 28-day screening period, a 12-week treatment period, and subsequently a 28-day follow-up period. Each patient will have 6 visits and unscheduled visits as needed.

Approximately 150 patients (2 x 50 patients MP1032 and 50 patients placebo) who meet the entry criteria will be randomized on Day 1 to receive either 150 mg MP1032, 300 mg MP1032 or placebo orally twice daily for 12 weeks.

Efficacy and safety will be assessed as outlined in the trial flow chart (see Table 2)

Patient Identification

Upon signature of informed consent (screening period) each patient receives a 5-digit patient identification number, which is composed of:

Digits 1 and 2: trial center (01, 02, 03, etc.) 01 – 10 for German sites and 11 – 20 for Polish sites

Digits 3, 4 and 5: individual screening number within the center (consecutively in the order of screening within the center: 001, 002, etc.)

Treatment Assignment

Patients will be randomized on a 1:1:1 basis to one of three treatment groups:

- MP1032 300 mg bid
- MP1032 150 mg bid
- Placebo bid

The trial will use a block randomization scheme. Enrollment will be performed competitively between all 14 centers (Germany and Poland) until approximately 150 patients are enrolled in the trial in order to have 120 evaluable patients.

Patients who are eligible for enrollment into the trial will be randomized at Visit 2/Day 1 and will be assigned the lowest random number available at the site. Patient kits will be dispensed according to the kit number assigned by the Interactive Web Response System (IWRS). The kit numbers will be assigned to the treatment kits by a simple randomization.

The treatment group designation will remain blinded until the final database is locked. If the blind is broken via IWRS, the date, time, person who broke the blind and the reason must be recorded in the patient's eCRF, and any associated AE report.

The random list, assigning the randomization number to the treatment groups, and the kit number list, assigning the kit number to the treatment groups will be generated by psy consult scientific services.

2.2 Sample size justification

It is planned to recruit approximately 150 patients for this clinical trial in Germany and Poland (each country approximately 75 patients) to achieve 120 evaluable patients.

No formal sample size calculations were performed for this explorative trial. A sample size of 40 in each group is adequate to detect a difference in rates (in PASI 75% or PGA improvement) of at least 0,274, e.g. a success rate of 0,674 (67,4%) in the active group and 0,4 (40%) in the placebo group, with 80% power, using a two group χ^2 test with a 0,100 two-sided significance level.

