6.4 Rationale for the sample size

It is planned to recruit approximately 150 patients for this clinical trial in Germany and Poland (each country approximately 75 patients) to achieve 120 evaluable patients.

No formal sample size calculations were performed for this explorative trial. A sample size of 40 in each group is adequate to detect a difference in rates of at least 0,274, with 80% power, using a two group χ^2 test with a 0,100 two-sided significance level.

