3.3 Analysis populations

3.3.1 Efficacy populations

Intent-To-Treat (ITT)

The full-analysis-set (FAS) will include all randomized patient who received at least one dose of IMP, and had at least one post-baseline assessment. The intention-to-treat (ITT) analysis will be based on the FAS. The FAS is considered primary analysis set for the efficacy analysis.

Per-Protocol (PP)

The valid-cases-set (VCS) will include all patients from the FAS, who completed the assessments of the co-primary endpoints without any protocol violation interfering with the precise evaluation of treatment efficacy and with sufficient exposure to IMP, i.e.

- who completed the visit 5 (Day 84) assessments of PASI and PGA;
- who did not take any prohibited concomitant medications up to the visit 5 (Day 84).

During the blind data review meeting (BDRM) concomitant medications will be reviewed considering timing, duration of concomitant treatment, and influence on the efficacy assessments to determine prohibited medication usage that warrants exclusion from the VCS;

- who were compliant with the dosing regimen. A subject will be considered compliant, if the subject administered $\geq 80\%$ of the planned capsules.

Subjects who prematurely discontinue the treatment due to an adverse event at least possibly related to IMP will not be excluded from the VCS.

Prior to breaking the blind, other additional criteria may be added to the list to accommodate for unforeseen events that occurred during the conduct of the trial that result in noteworthy study protocol violations.

The per-protocol (PP) analysis will be based on the VCS. Primary efficacy endpoints will be evaluated on VCS to assess the sensitivity.

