3.4 Statistical methods

Statistical analyses will be performed using two-sided tests, without adjustment for multiplicity. All p-values will be interpreted descriptively.

Data will be summarized by treatment group (and by visit when applicable), with respect to demographic and baseline characteristics, efficacy variables, and safety variables.

Summary statistics will include the mean, number of non-missing cases (n), standard deviation, median, minimum, and maximum values for continuous variables, and frequencies and percentages for categorical variables.

Categorical efficacy variables will be analyzed using the Cochran-Mantel-Haenszel (CMH) test with stratification by (pooled) analysis center and the Fisher's exact test in case of analyses without stratification (mainly for safety assessment).

Selected scores will be analyzed using an analysis of covariance (ANCOVA) model, with treatment group and (pooled) analysis center as factors and baseline outcome as covariate.

Time to event data will be analyzed using the Kaplan-Meier method, and treatment group differences will be tested by the log-rank test.

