3.4.6.2 Statistical analyses

Primary efficacy endpoints

The co-primary endpoint response in PASI 75 at Week 12 (Day 84) is defined as 75% improvement in PASI score compared to baseline (i.e. percent of change from baseline $\leq 75\%$). The co-primary endpoint improvement in PGA at Week 12 (Day 84) is defined as reduction by 1 or more points on the PGA scale in comparison to baseline.

The comparisons of the treatment groups MP1032 300 mg bid and MP1032 150 mg bid, each vs. the placebo treatment, with respect to each, the PASI 75 rate and PGA improvement rate, at Week 12 (Day 84) will be evaluated by the CMH test stratified by (pooled) analysis center. The common odds-ratio with 95% confidence interval will be provided. The homogeneity of the individual odds-ratios will be assessed by the Breslow-Day test.

Secondary efficacy endpoints

Secondary efficacy endpoints will be evaluated descriptively. The methodology outlined at the top of this section 3.4.6.2 will be applied for pairwise treatment comparisons vs. placebo:

The PASI 50 responder rate at Week 12 (Day 84) will be evaluated according to the primary efficacy endpoints, as well as the PASI 75, PASI 50 and PGA improvement at Week 4 (Day 28) and Week 8 (Day 56) of the treatment phase and at follow-up, 4 weeks after end of treatment.

The change in the PASI score from baseline to each post baseline visit, respectively, will be evaluated using an analysis of covariance (ANCOVA) model, with treatment group and (pooled) analysis center as factors and baseline outcome as covariate, in both analysis sets, FAS and VCS.

The time to achievement of PASI 50 and PASI 75, respectively, will be evaluated using the Kaplan-Meier method. The study day of first achievement of PASI 50 and PASI 75, respectively, will be the considered event, with study day of last assessment as the time point of censoring, in case of no occurrences of PASI 50 or PASI 75. Pairwise treatment group differences will be tested by the log-rank test.

Location shift in change from baseline in PGA will be assessed using Hodges-Lehmann Estimation with comparison by the Wilcoxon rank sum test, in both analysis sets, FAS and VCS.

Descriptive summaries will be provided for each parameter by treatment group and by visit, if applicable. Percentages will be provided based on the number of non-missing cases, if not otherwise stated. For PASI and PGA the descriptive summaries will be performed in both analysis sets, FAS and VCS.

Subgroup analyses

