3.5.1 Missing data

A description of missing data will be provided in the clinical study report.

For the evaluation of success rates of the primary efficacy variables PASI and PGA missing PGA assessments and/or any parts of the PASI assessments will be evaluated as failure to achieve improvement.

For descriptive analyses of PASI, PGA and BSA the last observation carried forward (LOCF) principle will be applied to impute the missing assessments, up to the Day 84 visit. Follow-up assessments will not be imputed.

Sensitivity of the primary efficacy analyses will be evaluated applying PP analyses.

Regarding incomplete recordings for adverse events the following rules apply:

- For start and stop dates no imputation will be applied. If any, start or stop date, is not complete, but required for the classification, i.e. the occurrence of the AE is not explicitly reported as occurring prior first dose (see eCRF), the AE will be considered treatment emergent.
- Missing assessments of severity, intensity and causal relationship to the IMP will be reported as a separate category.

For the determination of the number of years from start of psoriasis to the screening visit missing starting days will be imputed by the first day of month and missing months will be imputed by the first month (January) of the year.

For concomitant therapies (see section 3.2.2.4) incomplete dates will not be imputed. If an incomplete start or stop date does not allow for the classification as prior and/or concomitant therapy - despite of information in eCRF if taken/used prior to first dosing and/or if ongoing at first dosing - the treatment will be reported as prior and as concomitant therapy.

Pharmacokinetic data below LLQ will be replaced as described in 3.4.7.3 for descriptive statistics and for the derivation of $AUC_{(0,t)}$. Missing pre-dose levels will be imputed by zero. Missing intermediate samples, i.e. missing values in between non-missing levels (quantifiable or substituted by LLQ/2) will be imputed by linear interpolation between the last preceding and the next following available value. The last value will be imputed by LLQ/2, if missing.

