3.5.3 Unscheduled visits

If applicable, the reason for unscheduled visit assessments will be given together with the results. For the statistical analysis the unscheduled assessments will be assigned as described in section 3.5.2.

In case of premature withdrawal from the trial, efficacy assessments performed at the time point of withdrawal, will be assigned to a planned visit as described in section 3.5.2.

Safety assessments performed at the time point of withdrawal will be reported together with the last visit in treatment phase (Day 84 / End of Treatment [EoT]).

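### Does SAP 2.2 need a power figure for the full-analysis-set comparison with its 95% confidence interval?

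*SAP*

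**What the plan says.** Protocol 6.4 states that "A sample size of 40 in each group is adequate to detect a difference in rates of at least 0,274", with 80% power by a two-group chi-square test at a two-sided 10% level. SAP 2.2 repeats this ("A sample size of 40 in each group is adequate to detect a difference in rates") and adds example rates of 67.4% on active treatment and 40% on placebo. Both sections plan to recruit about 150 patients "to achieve 120 evaluable patients", that is 40 of about 50 per arm, and both say that no formal sample size calculation was made because the trial is explorative.

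The primary analysis is described elsewhere in the SAP:

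- Section 3.3.1: "The FAS is considered primary analysis set for the efficacy analysis". Entry to the FAS needs one dose and one post-baseline assessment, not Day 84 data.
- Section 3.5.1: a missing PGA, or a missing part of the PASI, "will be evaluated as failure to achieve improvement".
- Section 3.4.6.2: a Cochran-Mantel-Haenszel (CMH) test stratified by pooled centre. "The common odds-ratio with 95% confidence interval will be provided".
- Section 3.4: tests are two-sided and unadjusted, with no numerical level. "All p-values will be interpreted descriptively". Section 3.4.6.1 states that there are no formal hypotheses.

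**The concern.** The power statement and the primary analysis do not describe the same thing. The 40 per arm are evaluable patients, a term neither document defines, whereas the FAS can hold about 50 per arm, some without Day 84 data. The 10% level appears only in the sample-size text, whereas the effect is reported with an interval that corresponds to 5%. The SAP does not say whether 0.674 and 0.40 already count missing outcomes as failures, and it gives no expected missing rate.

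What is at stake is interpretation. A reader who sees 80% in SAP 2.2 and then a 95% interval that includes an odds ratio of 1 might take the result as stronger evidence of no effect than it is.

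**Working it through.** **Inputs from the documents.** Rates p1 = 0.674 and p2 = 0.40 (SAP 2.2), so d = 0.274; n = 40 per arm; two-sided level 0.10; about 50 randomised per arm (SAP 2.1).

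**Inputs assumed.** A 5% level, inferred from the 95% interval. A missing share m of 0 to 20%, equal in both arms. Placebo rates other than 0.40.

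**Step 1. Reproduce the stated figure.** With the usual pooled-variance formula,

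n = [z(α/2)·√(2·p̄·q̄) + z(β)·√(p1q1 + p2q2)]² / d²

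p̄ = 0.537, so √(2 × 0.537 × 0.463) = 0.7052, and √(0.2197 + 0.2400) = 0.6780.

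- At 10%: (1.645 × 0.7052 + 0.842 × 0.6780)² / 0.274² = 39.9, so 40 per arm.
- Power at n = 40: Φ[(0.274 × √40 − 1.645 × 0.7052) / 0.6780] = Φ(0.845) = 80.1%. Exact enumeration of the chi-square test gives 79.2%.

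The plan's figure is right.

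**Step 2. Does it hold at other placebo rates?** Protocol 6.4 claims a 0.274 difference without naming rates. For n = 40 at 10%, power is 90.4%, 83.9%, 80.5%, 80.1% and 82.7% at placebo rates of 0.10, 0.20, 0.30, 0.40 and 0.50. The minimum, 79.9%, is at 0.363, where the two rates (0.363 and 0.637) are symmetric about one half. The SAP's example is therefore close to the worst case.

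**Step 3. The 5% level.** For 0.674 against 0.40 with n = 40, power is Φ[(1.733 − 1.960 × 0.7052) / 0.6780] = Φ(0.517) = 69.8% (exact 71.9%). By the formula, 80% would need 50.8, so 51 per arm. With a placebo rate of 0.10 the same 40 per arm give 83.5%.

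**Step 4. FAS of 50 per arm, missing counted as failure.** Take the example rates as rates among patients with Day 84 data and multiply both by (1 − m):

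| m | Rates | Power at 10% (exact) | Power at 5% (exact) |
|---|---|---|---|
| 0 | 0.674 vs 0.400 | 87.4% (86.4%) | 79.4% (81.0%) |
| 5% | 0.640 vs 0.380 | 84.0% | 74.8% |
| 10% | 0.607 vs 0.360 | 80.2% (78.8%) | 70.0% (72.2%) |
| 15% | 0.573 vs 0.340 | 76.2% | 65.1% |
| 20% | 0.539 vs 0.320 | 72.0% (71.2%) | 60.3% (62.2%) |

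By the formula, power at 10% falls below 80% at m = 10.3%. Simulated CMH tests with 1 to 10 equal strata and no centre effect, run at m = 0 and m = 20%, gave about 71 to 87% at the 10% level and 62 to 81% at 5%, in line with the exact values. With a placebo rate of 0.10 and 20% missing, power is 88.5% at 10% and 80.8% at 5%.

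**Step 5. Which row applies?** The documents do not say.

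- If 0.674 and 0.40 already count missing as failure, the first row applies whatever the missing rate.
- If the 30 patients between 150 and 120 have no post-baseline assessment, they leave the FAS. It then holds 40 per arm, with 80% power at 10% and 70% at 5%.
- The 20% row needs all 30 to stay in the FAS without a Day 84 value. SAP 3.5.3 makes that less likely, because "efficacy assessments performed at the time point of withdrawal, will be assigned to a planned visit as described in section 3.5.2", so some early leavers will have a value assigned to Day 84.

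**The case for a change.** The strongest case for a change is that the SAP prints 80% power and a 95% interval, and readers will put the two together. With 40 per arm and the sponsor's own rates, a test at 5% misses a true 27-point difference about 30% of the time (100 − 69.8; 28% by exact enumeration), not 20%. The larger FAS only partly offsets this: at 5%, power is about 80% with nothing missing and falls from there. A few sentences defining evaluable patients, stating what the example rates represent and giving a range would remove the doubt at little cost.

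The facts in this stand. Evaluable is undefined, 10% is a planning level that appears nowhere else, and the 5% power is lower.

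The inference does not follow. Missing an effect presupposes a decision rule, and the SAP has none: no hypotheses, no test level, and no statement that an interval including 1 means failure. The interval conveys its own precision whatever power was quoted beforehand. The low end of the FAS range depends on a 20% missing rate that the plan does not state. It also depends on the missing-as-failure rule of SAP 3.5.1, while the responder table shells (Tables 14.3.3 and 14.3.15) are titled as last observation carried forward. That conflict is a separate matter. Until it is settled, writing FAS power into SAP 2.2 would add figures resting on an unresolved rule.

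**Conclusion.** No change follows. The only power statement in the plan is correct for the case it describes: 80.1% at the example rates and at least about 79.9% for a 0.274 difference at any placebo rate. At the plan's own 10% level, an FAS of 50 per arm matches or exceeds 80% up to about 10% missing, even on the less favourable reading of the example rates.

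The lower figures (about 70% at 5% with 40 per arm, or 60 to 79% at 5% in an FAS of 50) are valid calculations, but they rest on a decision level, a missing rate and a reading of the rates that the documents do not supply. The missing detail could be written down, and 90% intervals could be shown beside the 95% ones, but neither would change enrolment, the primary analysis or the conclusions of a trial declared exploratory and descriptive. An analyst can treat the 80% as a planning figure and read the reported interval directly.

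The conclusion assumes that the trial is reported as the SAP describes. If a 95% interval including 1 were used as a formal stop rule, the 70% figure would matter.
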